### **PROGRAMMING CONVENTIONS AND STANDARD CALCULATIONS:**

#### **Partial and Missing Dates**

If only a partial date is available, and it is required for analysis (for example, duration or time to event analysis), the following general imputation rules will be applied. More details will be provided below for each specific safety endpoints.

- Start date:
  - For missing day only – Day will be imputed as the first day of the month (ie, 1).

- For missing day and month – Day and month will be imputed as the first day of the year (ie, 1 January).
- Missing dates will not be imputed
  
- Stop date:
  - For missing stop day only - Day will be imputed as the last day of the month (ie, 28, 29, 30, or 31).
  - For missing stop day and month - Day and month will be imputed as the last day of the year (ie, 31DEC).
  - Imputed stop dates must be on or after the start date.

#### Partial Date Imputation by Safety Endpoints:

- Diagnosis date: Follow the general imputation rules above for start date
- Concomitant medication Start date: Follow the general imputation rules with the following exceptions:
  - If the partial date falls in the same month and year as the first dose date, then the partial date will be imputed to equal the first dose date
  - If the partial date falls in the same year as the first dose date, then the partial date will be imputed to equal the first dose date
  
- Investigational Product (OCA): Consider only exposure records with non-missing dose.
  - If start date is partial or missing, then start date = non-missing stop date of the preceding exposure record +1 if there is a preceding record (including interruptions and drug holiday). If both dates are partial, choose the date in the middle after imputing the earliest date as the first day in the month and the latest date as the last day in the month.
  - If stop date is partial or missing, then stop date = non-missing start date of the following exposure record -1. If both dates are partial, choose the date in the middle after imputing the earliest date as the first day in the month and the latest date as the last day in the month.
  - Missing stop date in the last exposure record will be imputed by the earliest of
    1. Last exposure date in the EOT/EOS CRF.
    2. End of treatment visit date
    3. Last visit before the end of treatment
    4. End date of study discontinuation, death date or data-cutoff date

- Adverse Events:
  - Missing start day of the first record of AEs with the same system organ class (SOC) and preferred term (PT): Day will be imputed as the first day of the month with the following exception: if the partial date falls in the same month and year as the first dose date, then the partial date will be imputed to equal the first dose date.
  - Missing start day and month of the first record of AEs with the same system organ class (SOC) and preferred term (PT): Day and month will be imputed as the first day of the year with the following exception: if the partial date falls in the same year as the first dose date, then the partial date will be imputed to equal the first dose date
  - Imputed start dates must be prior to the stop date.
  - Missing stop day only: Day will be imputed as the latest of the last day of the month (ie, 28, 29, 30, or 31).
  - For missing stop day and month - Day and month will be imputed as the last day of the year (ie, 31DEC). Imputed stop dates must be on or after the start date.

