## **10.2. Prior and New Concomitant Medications**

Verbatim terms on eCRFs will be mapped to Anatomical Therapeutic Chemical (ATC) class and Preferred Name using the WHO Drug Dictionary Enhanced.

Pretreatment concomitant medications are those medications with start and stop prior to the initial dose of investigational product also classified as no concomitant medication. Prior concomitant medications are those medications started prior to and continued after the initial dose of investigational product. New concomitant medications are those medications that were started after the initial dose of investigational product. If it cannot be determined whether the medication was a new concomitant medication due to a partial start or stop date or if the medication is taken on the same date as the initial dose of investigational product, then it will be counted as a new concomitant medication.

No concomitant, prior, and new concomitant medications will be summarized separately for each treatment group by WHO ATC level 2, WHO ATC level 4, and preferred name using the Safety Population. These summaries will present the number and percentage of subjects using each medication. Subjects may have more than one medication per ATC level and preferred name. At each level of subject summarization, a subject is counted once if he/she reported one or more medications at that level. Each summary will be ordered by descending order of incidence of ATC level and preferred name within each ATC level.

Extent of exposure of newly initiated use (after the 1st dose) of vitamin E, thiazolidinediones, bile acid sequestrants (BABR), statins and other lipid-lowering medications, will be calculated as follows:

$$\text{Exposure to the concomitant medication} = \{[(\text{Date of last dose} - \text{Date of 1}^{\text{st}} \text{ dose}) + 1] - \text{Total duration of temporary interruptions}\}$$

Missing start and end dates will be imputed as described in [Appendix A](#). Extent of exposure will be summarized by treatment group as described in the General Statistical Methods ([Section 4](#)).

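### SAP Appendix A: the same-year exception for concomitant-medication start dates omits the condition that day and month are both missing, so read literally it replaces a known month with the first-dose date.

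*SAP*

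**What the plan says.** SAP Appendix A, under Partial and Missing Dates, sets two general rules for start dates. If only the day is missing: "For missing day only – Day will be imputed as the first day of the month". If day and month are both missing: "Day and month will be imputed as the first day of the year (ie, 1 January").

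Under Partial Date Imputation by Safety Endpoints, concomitant-medication start dates are told to "Follow the general imputation rules with the following exceptions". Two exceptions are listed:

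- Exception 1, which substitutes the first-dose date: "If the partial date falls in the same month and year as the first dose date, then the partial date will be imputed to".
- Exception 2, which substitutes that date as well: "If the partial date falls in the same year as the first dose date, then the partial date will be imputed to equal".

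The adverse-event rules in the same list also have a same-year exception, but it sits under an explicit condition: "Missing start day and month of the first record of AEs with the same system organ class (SOC) and preferred term (PT").

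SAP 10.2 defines the classes. "Prior concomitant medications are those medications started prior to and continued after the initial dose of investigational product". A drug whose status cannot be settled because of a partial date counts as new. A drug dated to Day 1 gets the same class: "if the medication is taken on the same date as the initial dose of investigational product, then it will be counted as a new concomitant". SAP 10.2 also summarises exposure to newly initiated vitamin E, thiazolidinediones, bile acid sequestrants, statins and other lipid-lowering drugs. That paragraph refers to Appendix A for imputed start and end dates.

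**The concern.** Exception 2 does not say that the month must be missing. A programmer who codes it as written will discard a known month for every partial start in the calendar year of first dose and substitute Day 1. Two kinds of record then go wrong: drugs started in a later month of that year are dated too early, and drugs started in an earlier month are dated too late.

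The dates feed the summary of exposure to newly initiated drugs in SAP 10.2. The split into no, prior and new use is a subgroup factor in SAP 4.4 for statins and antidiabetics (efficacy and safety) and for antihypertensives (safety). Statin timing is also used in SAP 10.4.3 for dyslipidemia events and in SAP 10.5.5 for lipoproteins. It matters here because protocol 9.3.3 expects LDL cholesterol to rise on OCA and recommends active lipid management, so when a statin was started is part of interpreting the lipid data.

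**Working it through.** The plan gives no figure to reproduce. The check applies the rule to example dates under two readings:

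- **Literal:** exception 2 covers any partial start in the first-dose year.
- **Qualified:** exception 2 covers only starts with both day and month missing, as in the adverse-event rule.

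Take first dose = 10 July 2017 (an illustrative date).

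| Recorded start | Literal | Qualified | What is known of the true start |
|---|---|---|---|
| Feb 2017 | 10 Jul 2017 | 1 Feb 2017 | 132 to 159 days before first dose |
| Jul 2017 | 10 Jul 2017 | 10 Jul 2017 | same month; order unknown |
| Nov 2017 | 10 Jul 2017 | 1 Nov 2017 | 114 to 143 days after first dose |
| 2017 only | 10 Jul 2017 | 10 Jul 2017 | order unknown |
| Mar 2014 | 1 Mar 2014 | 1 Mar 2014 | before first dose |

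Day counts: 28 February to 10 July is 31 + 30 + 31 + 30 + 10 = 132, and from 1 February it is 132 + 27 = 159. From 10 July to 1 November is 21 + 31 + 30 + 31 + 1 = 114, and to 30 November it is 114 + 29 = 143.

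**Later start (November).** SAP 10.2 computes exposure as last dose date minus first dose date plus 1, less interruptions. Each day of back-dating therefore adds one day of exposure. The literal reading adds 114 to 143 days that did not occur. The qualified reading adds 0 to 29.

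**Earlier start (February).** The imputed date is Day 1, which SAP 10.2 counts as new. But the month alone shows that the drug began before first dose, so if it continued after first dose the definition in SAP 10.2 makes it prior. The default for undeterminable dates does not apply, because the order is determinable. The two provisions give different answers for one record.

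**Redundancy.** Every date in the first-dose month and year also lies in the first-dose year, and both exceptions impute the same date. Under the literal reading exception 1 never changes a result.

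**Bounds.** Only starts in the first-dose calendar year are touched, so the displacement is at most 364 days (1 January against 31 December). Under the qualified reading it is at most 30 days for a known month.

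**Behaviour of the rule, not an estimate for this trial.** Take every pair of first-dose day and true start day in one 365-day year, equally weighted, with the month recorded: 365 × 365 = 133,225 pairs. Under the literal reading all pre-dose starts are put on Day 1, that is (365 × 364 / 2) / 133,225 = 66,430 / 133,225 = 49.9% of pairs. Post-dose starts are back-dated by 122 days on average. Under the qualified reading the corresponding results are 4.0% and 14 days.

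**The case against.** The best defence is that the literal reading is probably not what was meant. The general rules run in order: day missing, then day and month missing. The two medication exceptions follow the same order. Paired that way, each has a purpose and they match the adverse-event rules. This is a fair account of the likely intent, and it makes the defect a dropped qualifier rather than a deliberate rule. It does not remove the defect, because the text contains no such limit and programs are written from this appendix.

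Second, SAP 10.2 classifies by its own definition, and its reference to Appendix A stands in the exposure paragraph, not the classification paragraph. The SAP does not state that prior or new status is read from the imputed date. This stands: for an earlier-month start the documents conflict, and misclassification is not certain. Under the literal reading the back-dating of later starts does not depend on this point.

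Third, the consequences are limited. The rule is the same in every arm. SAP 10 plans no inferential safety comparisons unless specified, and the subgroups in SAP 10.5.5 are descriptive. Protocol 9.3 bars changes to TZDs and vitamin E for the first 18 months, so few such starts should arise in the affected year. All of this stands.

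A reader might infer more than the text supports:

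- That long-standing drugs in general turn into new use. They do not: a start in any earlier calendar year follows the general rule and stays before first dose.
- That dating year-only starts to Day 1 is an error. When the order cannot be determined, counting the drug as new is a stated convention in SAP 10.2.
- That about half of partial dates in this trial would be wrong. That share follows from assuming evenly spread dates, and the documents give neither a distribution nor a count.
- That drug-driven starts of lipid therapy would be hidden. Nothing in the documents shows this, and SAP 10.4.3 counts LDL rises directly.

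**Conclusion.** The point holds as a drafting error with a wrong result if followed as written. Exception 2 lacks the condition that the adverse-event rule carries. It therefore overrides a known month in the first-dose calendar year and makes exception 1 redundant. Later starts in that year are back-dated to Day 1 and inflate newly initiated exposure. Earlier-month starts receive a Day 1 date that SAP 10.2 counts as new, against its own definition of prior.

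For a single record the displacement can reach 364 days. The total effect in the trial is unknown because the number of partial dates is not given. The conclusion rests on the literal text, and the effect on prior or new status rests further on the class being taken from the imputed date. The primary time-to-event test does not use these dates. The issue is minor, but worth correcting before the analysis programs are final.

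**What to change.** In SAP Appendix A, restrict the second concomitant-medication exception to start dates with both day and month missing, in the same form as the adverse-event rule. State that where the month is known and differs from the first-dose month, the general rule applies and the start is set to the first of that month. Exception 1 can stay as it is.

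It would also help to say in SAP 10.2 whether prior or new status is taken from the recorded partial date or from the imputed date, so that the two sections cannot disagree.

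The cost is one or two lines of SAP text and a small programming change. No new data are needed.

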Subjects will be screened for a period of up to 12 weeks before entering the study. Approximately 2370 subjects with NASH who meet all eligibility criteria will be randomized to receive OCA 10 mg, OCA 25 mg, or matching placebo in a 1:1:1 ratio for the duration of the study, in conjunction with local standard of care. Randomization of subjects with fibrosis stage 2 or stage 3 will be stratified by presence of type 2 diabetes at enrollment (yes/no) and use of thiazolidinediones (TZDs)/glitazones or vitamin E at baseline (yes/no). Biopsy-confirmed NASH will be determined by central reading of liver histology at Screening, and all subsequent histology assessments will be performed centrally in a blinded fashion.

Investigational product (ie, OCA or placebo) will be taken orally, with water, once daily. Subject safety and laboratory assessments will be evaluated at clinical visits occurring after the first month and once every 3 months following the initiation of treatment (Day 1) through Month 18. Following the Month 18 visit, clinic visits will occur every 6 months for the remaining duration of the study.

With the exception of liver transplant, if a subject experiences a suspected or confirmed clinical outcomes event, he or she should continue the regular visit schedule and continue taking investigational product as long as the subject has not met any of the criteria for discontinuation outlined in [Section 7.7](#). Subjects who discontinue investigational product are expected to be followed through to study closure (or at the discretion of the Sponsor). Specific strategies to encourage continued subject participation in the study will be outlined in a Subject Retention Plan ([Section 7.9](#)).

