### 10.3. Adverse Events

AE data will be collected from the time that signed informed consent is obtained until the subject fully completes her/his study participation of the study. AEs will be reported and categorized using the Common Terminology Criteria for Adverse Events (CTCAE, Version 4.03).

All AE summaries will be restricted to TEAEs, which are defined as any AEs that newly appear, increase in frequency, or worsen in severity following randomization up to 30 days from the last dose date of permanent investigational product discontinuation up to new data cut-off date. If it cannot be determined whether the AE is treatment emergent due to a partial onset date, then it will be counted as such. Verbatim terms on eCRFs will be mapped to preferred terms (PT) and system organ classes (SOC) using MedDRA version 18.1 or later version.

Each AE summary will be displayed by treatment group. Summaries that are displayed by SOC and PT will be ordered by descending order of incidence (OCA 25 mg, followed by OCA 10 mg, followed by placebo) of system organ class and preferred term within each system organ class. Summaries of the following types will be presented:

- Overall summary of TEAEs
- Subject incidence of TEAEs and the total number of entries by MedDRA SOC and PT.
- Subject incidence of TEAEs and the total number of entries by PT in descending order.
- Subject incidence of serious TEAEs and the total number of entries by MedDRA SOC and PT.
- Subject incidence of TEAEs leading to investigational product withdrawal by MedDRA SOC and PT.
- Subject incidence of TEAEs leading to study discontinuation by MedDRA SOC and PT.
- Subject incidence of TEAEs by MedDRA SOC, PT, and highest severity (CTCAE grade). At each level of subject summarization, a subject is classified according to the highest severity if the subject reported 1 or more events. AEs with missing severity (CTCAE grade) will be considered grade 3 (severe) for this summary.
- Subject incidence and total number of entries of CTCAE grade 3 or higher TEAEs by MedDRA SOC and PT. At each level of subject summarization, a subject is

classified according to the highest severity if the subject reported 1 or more events. AEs with missing severity (CTCAE grade) will be considered grade 3 (severe) for this summary.

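### A missing last-dose date is set to the earliest of four dates, so a recorded last exposure date is displaced whenever dosing continued past the last visit before the end of treatment

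*SAP*

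**What the plan says.** The rule is in SAP Appendix A, under partial date imputation for investigational product: "Missing stop date in the last exposure record will be imputed by the earliest of" four listed candidates.

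- Item 1 is when exposure last occurred according to the EOT/EOS form.
- Item 2 is when the visit closing treatment took place.
- Item 3 is given as "Last visit before the end of treatment".
- Item 4 covers leaving the study, dying, or reaching the data cut-off.

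Appendix A does not say whether end of treatment in item 3 means the last dose or the end of treatment (EOT) visit.

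The resulting date is used widely. SAP Section 10.3 limits all adverse event summaries to treatment-emergent events (TEAEs), with a window running "following randomization up to 30 days from the last dose date of permanent investigational product discontinuation". The last dose date also enters censoring for TEAEs (SAP Section 4), subject exposure years (Section 10.4), pruritus patient-years (Section 10.4.1) and extent of exposure (Section 10.1).

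On visit spacing, Protocol Section 7.1 has a visit after the first month and then every 3 months through Month 18. After that: "Following the Month 18 visit, clinic visits will occur every 6 months for the remaining duration of the study". Protocol Section 9.9.1 sets a month at 28 days.

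**The concern.** The four items read like an order of preference, from the best source to the crudest, but the instruction is to take the smallest. The form field that exists to record the last dose then loses to a visit date from earlier in treatment.

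This also runs against the neighbouring conventions. In Appendix A, partial stop dates are pushed to the end of the month or year, and the last contact date for subjects lost to follow-up is the latest of several dates. Only the final dose date is pulled early.

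At stake are the safety tables. A subject who stops between visits because of an adverse event could have that event placed after the window. It would then be missing from the TEAE, serious TEAE and TEAE-leading-to-withdrawal summaries. The provision in SAP Section 10.3 that counts doubtful events as treatment-emergent covers only a partial adverse event onset date, not an imputed last dose.

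**Working it through.** The plan gives no figure for this rule, so there is none to reproduce. The check has two parts.

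**Logic of the minimum.** Write d1 to d4 for the four dates.

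- Item 3 is a visit earlier than the EOT visit on either reading, so d3 < d2. The EOT visit date cannot be selected if an earlier visit exists.
- If dosing continued past the visit in item 3, then d3 < d1, and the recorded last exposure date is displaced.
- If a subject is still dosing at the data cut-off, items 1 to 3 do not exist and item 4 applies correctly.

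**Size for an affected subject.** Inputs from the documents are the 28-day month, the visit schedule and the 30-day window. Assumptions that are not in the documents: stopping is uniform over the visit interval L, the imputed date is the preceding scheduled visit, and the event starts on the stop day. Then the mean shift is L/2, and the probability that the event lies outside the window is (L − 30)/L, or 0 if L is below 30.

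| Period | L (days) | Mean shift (days) | Event outside window |
|---|---|---|---|
| Day 1 to Month 1 | 28 | 14 | 0% |
| Month 1 to Month 3 | 2 × 28 = 56 | 28 | 26/56 = 46% |
| Month 3 to Month 18 | 3 × 28 = 84 | 42 | 54/84 = 64% |
| After Month 18 | 6 × 28 = 168 | 84 | 138/168 = 82% |

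**Relaxing the assumptions.**

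- Onset *a* days before stopping gives (L − 30 − a)/L. With a = 28: 26/84 = 31% and 110/168 = 65%.
- If a share *q* of subjects had an unscheduled visit within 30 days before stopping, the loss is (1 − q)(L − 30)/L. With q = 0.75: 0.25 × 54/84 = 16% and 0.25 × 138/168 = 21%.
- Suppose end of treatment means the EOT visit, held D days after the last dose. A scheduled visit can then fall between the two, and the recorded date survives. Displacement occurs with probability (L − D)/L, and loss with probability (L − D − 30)/L. With D = 42: displacement 42/84 = 50% and 126/168 = 75%; loss 12/84 = 14% and 96/168 = 57%. With D = 0, displacement is 100% and the loss is as in the table.

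**Under an order of preference.** If the form date is present and used, an event starting on or before the true last dose is never after the analysed last dose, so none is lost: 0%.

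**The case against.** The strongest reply has four parts.

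**Displacement is not universal.** A reader might infer that the recorded date is always overridden. The documents do not support that. End of treatment is undefined, and Protocol Section 7.7 lets an interruption become a discontinuation, with the EOT visit held only after discussion with the medical monitor. Protocol Section 7.4.1 sets a 30-day minimum interruption when liver tests remain elevated on repeat, with close monitoring. A visit between last dose and EOT visit is therefore plausible. This stands.

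**Loss may be uncommon.** A reader might also infer that the event causing the stop is often lost. The 64% and 82% figures assume onset on the stop day and no unscheduled visit. The protocol has subjects with potential hepatic injury brought in promptly (Section 7.4), renal triggers re-evaluated within 48 hours (Section 7.6.1) and safety visits at any time (Section 9.9.10). The rule also applies only where the final stop date is missing. No count is given, and data consistency checks (Protocol Section 18) should limit the number. This stands too: the figures are conditional.

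**Direction by arm.** It is tempting to conclude that harm on OCA would be understated. Protocol Section 5.3 reports 0, 0, 2 and 5 pruritus-associated discontinuations on placebo, 10, 20 and 40 mg in an earlier study, and Section 5.5 reports more frequent serious hepatic events on 25 mg. But missingness by arm is unknown. Earlier stop dates also shorten person-time for subjects without events, which raises exposure-adjusted rates. The net direction is open.

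**Safeguards exist.** Overall incidence of events of special interest is also shown for the whole study period (SAP Section 10.4), adjudicated cardiovascular times run from randomization (Section 10.4.9.1), and liver thresholds use any post-baseline visit (Section 10.5.4). The primary endpoint censors at last contact. These limit the damage, but none returns an event to the TEAE, serious TEAE or withdrawal tables.

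**Conclusion.** Wrong as written. The minimum gives a last-dose date that is too early whenever dosing continued past the visit in item 3, even if a better date is on the form.

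The size is known only per affected subject and only under assumptions. For an event starting on the stop day, the chance of leaving the window runs from 0% to 82% depending on the visit interval. It falls to 31% (84-day interval) or 65% (168-day interval) with onset 28 days earlier, and to 16% or 21% if three quarters of subjects had a recent unscheduled visit.

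The documents do not give the number of missing final stop dates, so the total effect on the safety tables cannot be stated. The primary efficacy analysis does not depend on this date.

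**What to change.** In SAP Appendix A, replace the minimum with the first available date in this order:

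1. last exposure date on the EOT/EOS form;
2. end of treatment visit date;
3. last visit before the end of treatment.

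Cap the result at the earliest of study discontinuation, death and data cut-off. Use that cap as the date when none of the three exists, as for subjects still dosing at cut-off. State whether end of treatment means the last dose or the EOT visit.

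The cost is one or two sentences and a programming change. Exposure and TEAE counts rise slightly for affected subjects. Where only the EOT visit date is available, exposure may be overstated by the gap between last dose and that visit, which the protocol asks sites to keep short.
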